Widely available technologies can help overcome the capacity constraints of brick-and mortar CMHCs, expand the reach of evidence-based mental healthcare, and provide much needed illness management skills and resources for people with SSD, wherever they may be. 12-14 People with SSD use smartphones and are interested in mHealth. Access and use of mobile technology is one of the few areas where gaps between people with SSD and the general population are narrow. In part due to the Federal Lifeline Assistance Program and the perpetually dropping costs of mobile phones and data plans, people with SSD in the U.S. now have broad access to mobile devices. 15 A recent meta-analysis found mobile phone penetration rates of 82% among people with SSD over the last three years with over a third owning smartphones.16 Survey research shows that the majority of people with SSD are open to receiving services and illness management support via their personal mobile devices and to sharing the information captured by technologies with their providers to support their care. 17-19 Evidence-based mobile health (mHealth) for SSD. mHealth interventions have emerged in all areas of healthcare including treatment and rehabilitation of people with severe psychiatric conditions. 20-22 Recent studies have demonstrated that a range of mHealth approaches, including clinical texting support, 23-25 behavioral sensing, 26, 27 and illness selfmanagement apps, 28-30 are feasible, acceptable, and clinically promising for people with SSD. With funding from the NIMH, PCORI, and CMMI, our group developed and tested FOCUS--a multimodal smartphone illness self-management system for people with SSD. A series of studies conducted with over 500 participants across ten US states has shown that FOCUS is feasible, usable, highly engaging, and effective among people with SSD 28, 31-37 (see Pilot Work for more details). Independent reviews of mHealth in Psychiatry have identified FOCUS to be one of the most carefully designed, optimized, comprehensive, and patient-centered mobile interventions for a defined clinical population. 37 FOCUS is ready for deployment in community mental health centers, however, optimal methods for providing mHealth treatment of SSD in real world practice settings are largely unexplored. Merely making digital health tools accessible (i.e., passive diffusion) will produce limited uptake and reach. Using targeted implementation strategies to engage CMHC providers will be crucial to integration of FOCUS in standard practice.38,39 Practice facilitation is an evidence-based implementation strategy, but one that has not yet been applied systematically to mHealth in CMHC settings. Practice Facilitation refers to the use of an individual (internal or external to a clinical setting) who carries out a specific role aimed at helping integrate evidence based interventions into practice. Practice facilitators work with providers and clinical organizations to make changes designed to improve patient outcomes. 40-42 A meta-analysis of 23 studies provides strong support for practice facilitation in primary care settings. 43 The Agency for Healthcare Research and Quality (AHRQ) has endorsed practice facilitation as an evidence-based approach. AHRQ notes that practice facilitators serve as key assets for innovation implementation in "Safety Net Practices" providing services to patients with chronic illness (defined by the Institute of Medicine as clinics that deliver healthcare and other services to uninsured, Medicaid and other vulnerable patients). 44 Safety Net Practices and CMHCs have multiple commonalities. We adapted core practice facilitation functions outlined in AHRQ's comprehensive practice facilitation curriculum 45 to develop two mHealth implementation models for CMHCs: External Facilitation (EF) (i.e., led by specialists who are not members of CMHC treatment teams), and Internal Facilitation (IF) (i.e., led by CMHC-embedded facilitators). Early versions of these models for implementation of FOCUS were shown to be feasible and acceptable to patients (see pilot work). The real-world implementation viability of these strategies to change the behavior of providers who work in CMHCs has not been evaluated. On the one hand, a few highly-trained and well-supervised external facilitators may be sufficient to engage many sites, creating opportunities for lowcost implementation on a large scale (e.g., hub-and-spoke model). On the other hand, there may be

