C. FOCUS: Effectiveness and readiness for implementation (pilot EF). We conducted a comparative effectiveness trial (RCT) 35 comparing FOCUS to a widely used an evidence-based group intervention (WRAP) in community mental health settings (n=163) (PCORI CER140311403). Results: FOCUS participants had better treatment commencement (90% vs. 58%), better continuous full engagement in treatment, equivalent (high) treatment satisfaction, and equivalent significant improvement in clinical outcomes: general psychopathology (SCL-9 Cohen's d=.44) depression (BDI-2 Cohen's d=.31), and recovery (RAS Cohen's d=.38). These moderate/large effects are clinically meaningful and comparable to more time/labor/resource intensive clinic based interventions.36 Patients rated the FOCUS intervention supported by EF as highly acceptable. Dropout in the FOCUS arm was very low (3.5%). Engagement was associated with clinical outcomes: more weeks of full engagement (defined as 5+ days of weekly use) were significantly associated with larger increases in recovery scores post-treatment. Patients who completed at least 8+ "fully engaged" weeks showed greater improvements in general psychopathology, depression, and recovery than those who did not. Relevance for implementation: CMHC providers and organizational leaders indicated a strong acceptability and interest in adoption and integration of mHealth in their programs. These findings were supported by responses to implementation survey items (rated 1-"Not at all" to 5-"Very Much"): I would be supportive of incorporating FOCUS into standard practice at my agency: M= 4.9; Connecting with clients through their smartphones would improve their quality of care: M=3.9; Connecting with clients through smartphone intervention would make me more effective in my job: M=4.25). Relevance for implementation: The FOCUS intervention required training and supervision of a single external facilitator who engaged with patients and supported and trained CMHC providers from a centralized location. The EF was not part of the CMHC clinical staff but hired and trained specifically for this role. 58 The clinical training materials and supervision structure was adapted and refined over the course of the 3-year study.

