5 PROCEDURES

study.

5.1 Study procedures. Using lay language, provide a complete description of the study procedures, including the sequence, intervention or manipulation (if any), time required, and setting/location. If it is available and you think it would be helpful to the IRB: Upload a study flow sheet or table to the **Supporting Documents** SmartForm in **Zipline**.

For studies comparing standards of care: It is important to accurately identify the research procedures. See UW IRB POLICY: Risks of Harm from Standard Care and the draft guidance from the federal Office of Human Research Protections, "Guidance on Disclosing Reasonably Foreseeable Risks in Research Evaluating Standards of Care"; October 20, 2014.

About the study:

This study is a multi-site site hybrid type III effectiveness/implementation study. The intention of this study is to examine the delivery of FOCUS within two treatment models. One, where the app is delivered through an internal facilitator embedded within a mental health clinic (study site), the other, involves an external facilitator delivering the intervention (staff at UW). Both facilitators help participants install, use, and incorporate the app's strategies into their own coping skillset.

The project will involve recruiting outpatients with schizophrenia spectrum disorder who receive mental health services at CMHCs in WA for participation in a randomized controlled trial (15 at each CMHC; n=300). Patient participants will engage in a 3-month long mHealth intervention called FOCUS which involves use of a smartphone system in their own environment and weekly phones calls with a practice facilitator that is based at the UW (EF model) or the CMHC where they receive care (IF model). Participants enrolled in the IF arm may also have in-person meetings with their agency-facilitator at their CMHC or in the community.

Arm I: All the same research procedures as ARM II, FOCUS delivery to participants is through an Internal Facilitator (staff member of study site who is identified and trained to serve as a navigator to the FOCUS app (technology, program use and application of strategies to their treatment plan)).

Arm II: All the same research procedures as ARM I, FOCUS delivery to participants is through an External Facilitator (UW staff who will be trained to serve as a navigator to the FOCUS app (technology, program use and application of strategies to their treatment plan)).

Description of the mHealth intervention:

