## UNIVERSITY of WASHINGTON

Analytic Approach. Our analyses seek to test the overall effect of our implementation strategies on implementation outcomes (Aim 1), mediators and moderators of those effects (Aim 2), and the impact of the strategies on patient outcomes (Aim 3). In Aim 1, the dependent variables of interest will be penetration and provider acceptability assessed at baseline (prior to initiation of the facilitation strategies), at 3 months (following the completion of the facilitation period), and at 6 months (following 3 months of having no exposure to facilitation). Given the nested data (i.e., time nested within clinicians and clinicians nested within agencies), analyses will rely on 3-level mixed effects regression models. Negative binomial regression with log offsets will be used to model rates, and linear regression will be used to model continuous outcomes. For all models, our independent variables of interest will be a binary indicator of internal versus external facilitation (measured at the organizational level), time, and their interaction. The magnitude and statistical significance of the interaction term will estimate the effect of the implementation strategy on change, or "growth," in outcomes over time. The impact of the intervention strategy on each outcome at each time will also be derived from these models. In addition, we will aggregate facilitylevel data and estimate the average weighted cost metrics across the sample of sites. Future commercial pricing of mHealth technology is unknown, so we will run scenarios that have different ranges of costs for FOCUS and explore the impact on the total program costs.

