In Aim 2, mediation will be tested using the product of coefficients approach for multilevel mediation analysis, building on the models in Aim 1. In this approach, the total effect of the implementation strategy is parsed into direct and indirect pathways associated with absorptive capacity, the mediator. Path "a" will represent the effect of the implementation strategy at the organizational level on the clinician-level assessment of absorptive capacity. Path "b" represents the relationship between this mediator and the clinician-level growth parameter, signifying change in outcomes over time. An unbiased estimate of the mediated effect is derived via the product of the "a" and "b" paths (i.e., a\*b) from these analyses. We will test the statistical significance of the mediated effects using the joint significance test and use Monte Carlo simulation methods to derive confidence intervals. Separate mediation models will assess whether absorptive capacity mediates the relationship between implementation strategy and, respectively, penetration, cost, and acceptability outcomes. Moderators of the implementation strategies' effects will be tested by adding terms for each hypothesized moderator and its interaction with the implementation strategy to the Aim 1 models. Specifically, these models will estimate the conditional relationships between the implementation strategies and implementation outcomes across different values of the putative moderators. Organization-level moderators (i.e., Readiness for Change, Organizational Culture, Urban or Rural designation) will be examined. The magnitude of the moderator effects will be probed using simple slopes analysis and region of significance analysis for multilevel models.

In Aim 3, we will use the same techniques as described in Aim 1 to develop 3-level linear mixed regression models that account for the nesting of time within patient and patient within organization to assess the impact of the implementation strategy on patient outcomes over time. We will use the methods described in Aim 2 to examine whether this relationship is moderated by organizational moderators and selected patient demographic characteristics (i.e., gender, race). We will also determine if patients' level of mHealth engagement mediates the relationship between implementation strategy and patient outcomes. All analyses will be conducted using MPlus to

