## UNIVERSITY of WASHINGTON

appropriately estimate multilevel regression models and to conduct Monte Carlo simulations. Our multilevel models in MPlus will allow us to accommodate likelihood-based ignorable analyses to obtain unbiased model inference without directly modeling drop-out associated with attrition.

Power Analysis. The sample size for the project is limited by the maximum number of organizations and clinicians that can be recruited within the logistical and financial constraints of an R01. With our available resources, we expect to enroll 20 CMHCs, with 5 clinicians per CMHC, and 3 patients per provider (n=300 patients, 100 providers). Based on our prior work (see Pilot Study B), we were able to calculate a between-organization ICC of 0.19 and a between-patient ICC of 0.45 for patientlevel outcomes similar to those being tested in this study. With an average of 15 patients per site, we will have 80% power to detect small to moderate effects of the implementation strategy on patient outcomes (Cohen's d=0.44). For provider-level outcomes, assuming a between-provider ICC of 0.30, we will have power to detect moderate effects of the implementation strategy (Cohen's d=0.55). Alpha is set at .05 (two-tailed) and will not be adjusted for multiple comparisons because we prefer to explore leads that may turn out to be wrong rather than miss potentially important findings. Using similar model assumptions, the study will have sufficient power to detect moderate effects of organizational-level moderators on patient outcomes (Cohen's d=0.50) and provider outcomes (Cohen's d=0.61). For the mediation analysis, the proposed sample size will yield sufficient power to detect a large indirect effect (Cohen's d=0.85) of the strategy through the practitioner-level mediators and a large indirect effect (Cohen's d=0.65) of the strategy through the patient-level mediators, assuming there is a moderate effect of the implementation strategy.

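### If external facilitators are shared across EF clinics, as seems likely, the SAP models omit that shared component and can understate the EF-IF standard errors

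*Protocol*

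**What the plan says.** Randomization is by clinic, with 20 clinics (Protocol 5.1, Study Sites). In the internal facilitation (IF) arm the facilitator is a member of the clinic's own staff. In the other arm, "FOCUS delivery to participants is through an External Facilitator", described as university staff (Protocol 5.1, Arm II).

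On staffing, the Protocol offers only indirect evidence:
- The background (Protocol 1.8a) says that "a few highly-trained and well-supervised external facilitators may be sufficient to engage many sites" and mentions a hub-and-spoke arrangement.
- The EF pilot (Protocol 1.8b, part C) "required training and supervision of a single external facilitator", who worked from a central location.
- Protocol 4.1 assigns each patient to the facilitator of the patient's site and does not say whether sites share one.

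The SAP (Analytic Approach) specifies three-level models. For Aim 1 the levels are "time nested within clinicians and clinicians nested within agencies". For Aim 3 the models "account for the nesting of time within patient and patient within organization". No facilitator level, random effect or sensitivity analysis appears, and the Power Analysis gives no facilitator ICC.

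**The concern.** The arms differ in structure. An internal facilitator belongs to one clinic, so that person's effect is already inside the clinic's random effect. An external facilitator who serves several clinics gives them a common component, and averaging over those clinics does not reduce it. The stated models treat the clinics as independent given arm, so this component is missing from the standard error of the EF mean.

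The trial is meant to inform a choice between two implementation models. If the component is omitted, chance differences between the few people employed as external facilitators can appear as a difference between EF and IF. With a single external facilitator, person and arm are completely confounded, and no model can separate them.

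**Working it through.** **Inputs from the documents.** 20 clinics, 15 patients per clinic, between-organization ICC 0.19, between-patient ICC 0.45, two-sided alpha 0.05, and 80% power for d = 0.44 on patient outcomes (SAP, Power Analysis). Three assessments (Protocol 5.1).

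**Assumptions.** 10 clinics per arm (no ratio is stated); m external facilitators spread as evenly as possible over the EF clinics; facilitator variance ρ of 0.01, 0.02 or 0.05, with total variance 1. The documents give neither m nor ρ.

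**Step 1: reproduce d = 0.44.** The detectable effect is (1.960 + 0.842) × √[(4/20) × (V_org + V_pat/15 + V_res/45)].
- *Split A*, 0.19 as a share of total variance: V_org = 0.19, V_pat = 0.45, V_res = 0.36. The bracket is 0.19 + 0.030 + 0.008 = 0.228, so the detectable effect is 2.802 × √0.0456 = 0.598, and power at 0.44 is 54%.
- *Split B*, 0.19 as a share of the 0.45: V_org = 0.0855, V_pat = 0.3645, V_res = 0.55. The bracket is 0.0855 + 0.0243 + 0.0122 = 0.1220, so the detectable effect is 2.802 × √0.0244 = 0.438, and power at 0.44 is 80.4%.

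Only split B reproduces the SAP figure, and it does so with all 20 clinics independent. Both splits are carried forward.

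**Step 2: add the facilitator.** Take ρ out of V_org, so that the variance of a single clinic is unchanged, and let c = V_pat/15 + V_res/45.
- True variance of the EF-IF difference: (V_org − ρ + c)/10 + ρ/m + (V_org + c)/10.
- Variance the analysis expects to estimate: [(V_org − ρ + c) + ρ(10/9)(1 − 1/m) + (V_org + c)]/10.

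Example, split B, ρ = 0.02, m = 1:
- True variance: 0.01020 + 0.02 + 0.01220 = 0.04240, SE 0.2059.
- Estimated variance: (0.10202 + 0.12202)/10 = 0.02240, SE 0.1497.
- Ratio of true to reported SE: 0.2059/0.1497 = 1.376.
- The critical value of t on 18 df, 2.101, becomes an effective 2.101/1.376 = 1.527, so the two-sided error is 14.4%.

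**Step 3: range.** Type I error from simulated clinic means (200,000 trials per cell, t test on 18 df), for ρ = 1% / 2% / 5%:

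| External facilitators | Split A | Split B |
|---|---|---|
| 1 | 7.3 / 9.8 / 17.6% | 9.6 / 14.4 / 28.0% |
| 2 | 6.1 / 7.1 / 10.4% | 7.0 / 9.0 / 15.9% |
| 3 | 5.5 / 6.3 / 8.2% | 6.2 / 7.4 / 11.4% |
| 5 | 5.2 / 5.5 / 6.3% | 5.5 / 6.0 / 7.6% |
| 10 | 5.0 / 5.1 / 5.0% | 5.0 / 5.0 / 5.0% |

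With one to five facilitators, the true SE is 1.01 to 1.89 times the reported one across both splits. Once the SE is put right, power at d = 0.44 under split B is 67 / 57 / 39% with one facilitator, 74 / 69 / 55% with two, 77 / 73 / 64% with three and 79 / 77 / 73% with five.

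**Step 4: is sharing plausible?** Ten EF clinics of 15 make 150 patients. At one call of 10-15 minutes a week (Protocol 5.1), all of them at once would need 25 to 37.5 call-hours weekly. A separate facilitator for each EF clinic would mean ten university staff with 2.5 to 3.75 call-hours each. That is possible, but it fits poorly with the hub-and-spoke rationale.

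**The case against.** The strongest reply is that sharing is never stated. The background sentence is about what might suffice at scale, the single facilitator belongs to an earlier trial, and the arm description gives only a role. This stands. A reader might infer that one or a few people are known to serve every EF clinic, and that type I error therefore exceeds 5% for every arm contrast. The documents support neither statement. With one facilitator per EF clinic, or with no facilitator variance, the planned standard errors are right.

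Four further points stand:
- If the target is the effect of EF as delivered by these particular people, the standard error is not understated for that target.
- The table is for a clinic-mean contrast. The SAP's principal test is arm by time, with baseline taken before facilitation starts. Stable clinic differences largely cancel from change, while a facilitator effect enters only afterwards. What matters is ρ relative to between-clinic variance in change, which is not given, so the percentages do not carry over in either direction. Nor do they cover the Aim 1 provider outcomes.
- The size depends on assumed values. With three or five facilitators at 1-2% it is small (5.2-7.4%).
- Estimating a facilitator random effect from very few people is not a dependable remedy. With three facilitators over ten EF clinics (4/3/3), clinic variance 0.19 and residual 0.81/15, an ANOVA estimate of the facilitator variance is zero or negative in 54%, 50% and 39% of trials at 1%, 2% and 5%.

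None of this supplies the missing term, and no passage gives each EF clinic its own facilitator.

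**Conclusion.** The point holds conditionally. The models have no facilitator component. Sharing is a strong inference from central university staffing, the stated rationale and the pilot, but it is not a documented fact. If facilitators are shared and their variance is above zero, EF-IF standard errors are too small for inference about EF as a strategy. For a clinic-mean contrast with 10 clinics per arm and ρ of 1-5% (both assumed), the two splits together give type I error of about 7-28%, 6-16%, 5.5-11.5%, 5-8% and 5% for one, two, three, five and ten facilitators. The direction is clear under those conditions. The size runs from negligible to serious and cannot be fixed until the number of facilitators is known. For the arm-by-time test it cannot be sized from the documents.

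**What to change.** 1. State how many external facilitators there are and which EF clinics each serves, and record facilitator ID for every clinic in both arms.
2. If any facilitator serves more than one EF clinic, pre-specify a sensitivity analysis that repeats the arm and arm-by-time contrasts with an EF-only shared facilitator variance fixed at 1%, 2% and 5% of the total. It should be zero at baseline and present at 3 and 6 months.
3. Estimate that variance as a random effect only with about five or more external facilitators, and with a small-sample correction.
4. With one or two external facilitators, state in the report that the EF-IF result is conditional on the people employed.

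The cost is one data field and wider intervals in the sensitivity analysis; no extra staff are needed. Assigning facilitators to EF clinics at random would help but would change trial conduct. It is optional and the fix does not depend on it.

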2 PARTICIPANTS

2.1 Participants. Describe the characteristics of the subject populations or groups, including age range, gender, health status, and any other relevant characteristics.

Patient participants will all be over the age of 18, include all genders, use English, own a smartphone with data plan has a diagnosis of schizophrenia-spectrum disorders and receive services from a participating clinic.

2.2Inclusion and exclusion criteria. Describe the criteria you will use to decide who will be included in your study from among interested or potential subjects. Define any technical terms in lay language.

Patient inclusion criteria: a) Chart diagnosis of SSD (i.e., schizophrenia, schizoaffective disorder, schizotypal disorder, delusional disorder, or schizophreniform disorder; b) 18 years or older; c) English-speaking; d) Own a smartphone that can support FOCUS and active data plan.

[figure not shown]
Patient exclusion criteria: 1) Used FOCUS in the past; 2) Plan to move or discontinue CMHC services in the upcoming 6 months.

CMHC staff will be asked to complete an online survey evaluating implementation outcomes and clinic characteristics. Staff from CMHC administration/budget/finance offices will also help inform costing through the use of de-identified data.

Staff inclusion criteria: a) Staff members at a participating study site; b) 18 years or older.

- **(2.3) Prisoners**. IRB approval is required in order to include prisoners in research, even when prisoners are not an intended target population.
 - a. Do you intend to deliberately recruit prisoners or obtain prisoner data/specimens?

See the WORKSHEET: Prisoners for the definition of "prisoner".

	b. Is your research likely to have subjects who become prisoners while participating in your study?		
	For example, a longitudinal study of youth with prisoners at some point during the study.	drug problems is likely to have subjects who will be	
	No Yes → If yes, if a subject becomes a prisoner while participating in your study, will you continue the study procedures and/or data collection while the subject is a prisoner? No Yes → If yes, describe the procedures and/or data collection you will continue with prisoner subjects		
2.4 Protected populations . IRB approval is required for the use of the subject populations listed here. Check the boxes for any of these populations that you will purposefully include in your research. (In other words, being a part of the population is an inclusion criterion for your study.)			
	The WORKSHEETS describe the criteria for approva	al.	
	Population	Worksheet	

Population	Worksheet
Children	WORKSHEET: Children
Children who are wards	WORKSHEET: Children
Cognitively impaired adults	
Fetuses in utero	WORKSHEET: Pregnant Women
Neonates of uncertain viability	WORKSHEET: Neonates
Non-viable neonates	WORKSHEET: Neonates
Pregnant women	WORKSHEET: Pregnant Women

[&]quot;Children" are defined as individuals who have not attained the legal age for consent to treatments or procedures involved in the research and its specific setting. This will vary according to the location of the research (that is, for different states and countries).

n or ised
m
į
ur
r but nts,
nd

2.7 Number of subjects. Can you predict or describe the maximum number of subjects (or subject units) you need to complete your study, for each subject group?

Subject units mean units within a group. For most research studies, a group will consist of individuals. However, the unit of interest in some research is not the individual. Examples:

- Dyads such as caregiver-and-Alzheimer's patient, or parent and child
- Families
- Other units, such as student-parent-teacher

Subject group means categories of subjects that are meaningful for your research. Some research has only one subject group – for example, all UW students taking Introductory Psychology. Some common ways in which subjects are grouped include:

- By intervention for example, an intervention group and a control group.
- By subject population or setting for example, urban versus rural families
- By age for example, children who are 6, 10, or 14 years old.

The IRB reviews the number of subjects you plan to study in the context of risks and benefits. You may submit a Modification to increase this number at any time after you receive IRB approval. If the IRB determines that your research involves no more than minimal risk: you may exceed the approved number and it will not be considered non-compliance. If your research involves more than minimal risk: exceeding the approved number will be considered non-compliance.

No → If no, provide your rationale in the box below. Also, provide any information you can about the scope/size of the research. You do not need to complete the table.

Example: you may not be able to predict the number of subjects who will complete an online survey advertised through Craigslist, but you can state that you will post your survey for two weeks and the number who respond is the number who will be in your study.

Yes \rightarrow If yes, for each subject group, use the table below to provide your estimate of the maximum desired number of individuals (or other subject unit, such as families) who will complete the research.

Group name/description	Maximum desired number of individuals (or other subject unit, such as families) who will complete the research *For clinical trials: provide numbers for your site and for the study-wide total number
Patients with SSD	300
Staff	200

